9.4.2 ANALYSIS OF THE PRIMARY EFFICACY ENDPOINT(S)

For each primary endpoint:

1. Change in the Anxiety score from State-Trait Anxiety Inventory

State anxiety will be assessed using the validated State-Trait Anxiety Inventory. The State-Trait Anxiety Inventory consists of 20 questions on a 4-point force-choice Like-type response scale (scores 0 - 3). The 20 questions are summed together for a final score. The score can range from 0 to 60 with higher scores representing higher levels of anxiety. Continuous, interval scaled sum scores will be calculated and treated as a repeated measure (assessed at weeks 8, 16, 20, and 24). Change in State-Trait anxiety inventory will be analyzed using two-way repeated-measures analysis for a time and treatment effect (proc mixed in SAS). Models will use an auto-regressive covariance structure to account for the repeated assessments in the same participants. Outliers at 2 SD's or more above or below the mean will be winsorized. Missing data will not be imputed, as the statistical procedures we will apply (proc mixed) are robust to randomly distributed missing data. Before applying proc mixed, we will check for the randomness of missing data. Results of the statistical procedures will be presented as adjusted means (least squared means) with standard errors.

2. Change in anhedonia score from Snaith-Hamilton Pleasure Scale

Anhedonia will be assessed using the validated Snaith-Hamilton Pleasure Scale (SHAPS). Scores range from 0-14, with higher scores corresponding to higher levels of anhedonia. The questionnaire will be applied at weeks 8, 16, 20 and 24. Continuous, interval scaled sum scores will be calculated and treated as a repeated measure (assessed at weeks 8, 16, 20, and 24). Change in the SHAPS will be analyzed using two-way repeated-measures analysis for treatment x week (proc mixed in SAS). Models will use an auto-regressive covariance structure to account for the repeated assessments of primary and secondary outcomes in the same participants. Outliers at 2 SD's or more above or below the mean will be winsorized. Missing data will not be imputed, as the statistical procedures we will apply (proc mixed) are robust to randomly distributed missing data. Before applying proc mixed, we will check for the

randomness of missing data. Results of the statistical procedures will be presented as adjusted means (least squared means) with standard errors.

9.4.3 ANALYSIS OF THE SECONDARY ENDPOINT(S)

All analyses of the secondary endpoints are independent of the primary endpoints.

For each secondary endpoint:

1. Changes in Cortisol stress response

The cortisol response will be presented as Area Under the Curve (AUC) with respect to ground and calculated using the trapezoid formula described by Pruessner¹⁷⁷. At weeks 8, 16, 20, and 24, cortisol was assessed around a standardized psychosocial stress test – the Trier Social Stress Test. Before the stress test, a baseline, pre-stress serum sample was taken. After the end of the stress test, reactivity serum samples were taken at 10-, 20-, 30-, and 45-minutes post-stress. The distribution of the values at every single timepoint, at every week will be visually inspected and, in case of skewness, log-transformed before calculating the AUC. All AUC's will be treated as continuous, interval scaled measures and treated as repeated measure (assessed at weeks 8, 16, 20, and 24). Results of the statistical procedures will be presented as adjusted means (least squared means) with standard errors. Outliers at 2 SD's or more above or below the mean will be winsorized. In case of missing values for one or more single timepoints around the stress task, the AUC will not be calculated and as a consequence treated as missing data. The statistical procedures we will apply (proc mixed) are robust to randomly distributed missing data.

2.&3. Changes in the EEfRT and Dot Probe task

Continuous, interval scaled sum scores will be used for statistical models testing changes in the EEfRT and the Dot probe task. Both scores will be treated as repeated measures (assessed at weeks 8, 16, 20, and 24). Results of the statistical procedures will be presented as adjusted means (least squared means) with standard errors. Outliers at 2 SD's or more above or below the mean will be winsorized. Missing data will not be imputed, as the statistical procedures we will apply (proc mixed) are robust to randomly distributed missing data.

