1.2 SCHEMA

Week 0

Medical Screening and Enrollment

- Obtain informed consent
- Screen potential participants by inclusion and exclusion criteria with online, phone, and medical screening via gynecological exam and mammogram
- Obtain history, document

Week 8

Lab Session- Baseline Assessments

- Administer STAI and SHAPS questionnaires
- Administer Dot Probe and EEfRT behavioral tasks
- Administer Trier Social Stress Test (TSST) and collect serum to measure cortisol at the end of baseline rest and at minutes 20, 30, and 45 of recovery post-TSST
- Urine HCG test to confirm subject is not pregnant prior to randomization

Randomization

- Active Intervention Group (0.10mg transdermal estradiol (E2))
- Placebo (matching inactive patch)
- Administer initial dose of study drug intervention

Week 16

Lab Session- Study Intervention, Side Effect & Compliance Checks

- Administer STAI and SHAPS questionnaires
- Administer Dot Probe and EEfRT behavioral tasks
- Administer Trier Social Stress Test (TSST) and collect serum to measure cortisol at the end of baseline rest and at minutes 20, 30, and 45 of recovery post-TSST
- Administer oral micronized progesterone (200mg daily)/matching placebo capsules for subjects to take for twelve days starting on Week 17 for the same treatment arms as E2/placebo randomization

Week 20

Lab Session- Study Intervention, Side Effect & Compliance Checks

- Administer STAI and SHAPS questionnaires
- Administer Dot Probe and EEfRT behavioral tasks
- Administer Trier Social Stress Test (TSST) and collect serum to measure cortisol at the end of baseline rest and at minutes 20, 30, and 45 of recovery post-TSST
- Continued administration of transdermal E2/placebo patch

Week 24

Final Lab Session- Study Intervention, Side Effect & Compliance Checks

- Administer STAI and SHAPS questionnaires
- Administer Dot Probe and EEfRT behavioral tasks
- Administer Trier Social Stress Test (TSST) and collect serum to measure cortisol at the end of baseline rest and at minutes 20, 30, and 45 of recovery post-TSST
- Administer oral micronized progesterone (200mg daily)/matching placebo capsules for subjects to take for twelve days starting on Week 25 for the same treatment arms as E2/placebo randomization
- Discontinue use of transdermal E2/placebo patch

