1.3 SCHEDULE OF ACTIVITIES (SOA)

Procedures	Medical Screening and Enrollment Week 0	Lab Session- Baseline Assessments & Randomization Week 8	Lab Session- Study Intervention, Side Effects, and Compliance Checks Week 16	Lab Session- Study Intervention, Side Effects, and Compliance Checks Week 20	Final Lab Session- Study Intervention, Side Effects, and Compliance Checks Week 24
Informed consent	X				
Demographics	X				
Medical history	X				
Physical and gynecological exam (including height and weight)	X				
Screening mammogram	X				
Pregnancy test ^a		X			
Randomization		X			
Administer transdermal estradiol/placebo		X	X	X	
Administer micronized progesterone/placebo			X		X
Discontinue transdermal estradiol/placebo					X
Administer STAI and SHAPS questionnaires		X	X	X	X
Administer Dot Probe and EEfRT behavioral tasks		X	X	X	X
Administer Trier Social Stress Test (TSST) and collect serum to measure cortisol ^b		X	X	X	X
Adverse event review and evaluation		X	X	X	X

a: urine pregnancy test (women of childbearing potential)
 b: serum collected at the end of baseline rest and at minutes 20, 30, and 45 of recovery post-TSST

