The Trier Social Stress Test (TSST) involves social evaluation of speech and serial subtraction stress and induces large HPA axis responses 122-125. Baseline Rest (30 mins): The subject will rest for 30 minutes. Instructions: (5 min) Subjects are introduced to a 2-person committee. The subject will assume the role of a job applicant who is invited for a personnel interview with the committee. Anticipation: The subject prepares for 10 min. Speech: The committee asks the subject to deliver her talk for 5 mins. The committee responds with prepared questions to ensure that the talk lasts for 5 mins. Serial Subtraction: The subject is given a number to start from and asked to subtract a number from that original number as fast and as accurately as possible for 5 mins. For each mistake, the subject restarts at the original number. Stress Recovery: The subject rests alone for 45 mins. The characteristics of the TSST that elicit large HPA axis response include: 1) lack of controllability; 2) creation of a context of forced failure; and 3) social evaluative threat²⁸. Thus, the TSST provides a physiologic unit of analysis for the construct of threat responsivity. To minimize habituation, we will use the second TSST at baseline week 8 as the comparison for all analyses (the first TSST will be used to eliminate the novelty effect). Modifications with each TSST will minimize habituation:¹²⁶ 1) a different speech topic, such as modifying the job; describing one's positive and negative personality attributes and impact on likeability¹²⁶; 2) different numbers in the serial subtraction; 3) different, opposite sex committee members each time. With these modifications, some novelty is maintained even with repeat exposure, ensuring a significant HPA response.

Neuroendocrine Sampling during Stress Testing: Plasma cortisol will be taken at the end of baseline rest and again during Recovery at minutes 20, 30, and 45, wince HPA-axis reactivity is reliably seen 10-30 minutes after cessation of the TSST ^{22,26}.

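### Section 9.4.3 lists a 10-minute cortisol sample that the procedural sections omit, and its log-transformation rule does not require one common scale for the AUC

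*Combined protocol and SAP*

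**What the plan says.** Section 9 states that there is no separate SAP, so its subsections are the analysis plan.

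**Sampling times.** Section 9.4.3 describes one pre-stress sample and then: "After the end of the stress test, reactivity serum samples were taken at 10-, 20-, 30-, and 45-minutes post-stress". Three procedural places agree with each other and differ from this:

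- Schema (1.2), at each of weeks 8, 16, 20 and 24: "collect serum to measure cortisol at the end of baseline rest and at minutes 20, 30, and 45 of recovery post-TSST".
- Schedule of Activities (1.3), footnote b: "serum collected at the end of baseline rest and at minutes 20, 30, and 45 of recovery post-TSST".
- Section 8.2: "Plasma cortisol will be taken at the end of baseline rest and again during Recovery at minutes 20, 30, and 45".

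**Measure and missing values.** "The cortisol response will be presented as Area Under the Curve (AUC) with respect to ground", by the trapezoid formula. "In case of missing values for one or more single timepoints around the stress task, the AUC will not be calculated"; that session's AUC is then treated as missing.

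**Scale.** In 9.4.3 the cortisol distributions "at every single timepoint, at every week will be visually inspected and, in case of skewness, log-transformed before calculating the AUC". Section 9.4.1 has a similar rule for values before and after each stress test. Neither section gives a skewness threshold, says that one decision covers all timepoints and weeks, or says that the decision is made blind to arm.

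**Hypothesis.** Section 9 plans a test of time as well as of treatment by time. For cortisol, H1 in 9.1 is a change from week 8 on active treatment and none on placebo; 9.4.1 repeats that expectation for all outcomes.

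**The concern.** There are two separate gaps in the definition of one secondary endpoint, the measure that carries the HPA-axis part of the central hypothesis.

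First, the analysis section and the procedural sections disagree about which samples exist. An AUC depends on its sampling grid, so the endpoint is not fixed until the list is. The missing-value rule makes the disagreement operational, because it needs a list against which a sample can be missing.

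Second, skewness is judged distribution by distribution, and logging comes before the AUC is formed. With four samples at four visits there are 16 distributions. If some are logged and others not, a single AUC can add raw and log units, or week 8 can sit on one scale and a later week on another. The AUC then moves between weeks for a reason that has nothing to do with cortisol, and it moves in both arms. A null result on placebo, which H1 requires, could not then be judged.

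**Working it through.** The plan states no figure for the cortisol AUC, so there is none to reproduce.

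**1. Timeline (Section 8.2).** Instructions 5 + anticipation 10 + speech 5 + serial subtraction 5 = 25 minutes from end of rest to end of stress. With end of rest at time 0, post-stress minutes 10, 20, 30 and 45 fall at 35, 45, 55 and 70.

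**2. Trapezoid weights.** An interior point has weight (next time − previous time)/2; an end point has half its adjacent interval. Both grids total 70 minutes.

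| Sample | Four-point weight | Share | Five-point weight | Share |
|---|---|---|---|---|
| End of rest | 22.5 | 32.1% | 17.5 | 25.0% |
| 10 min | – | – | 22.5 | 32.1% |
| 20 min | 27.5 | 39.3% | 10.0 | 14.3% |
| 30 min | 12.5 | 17.9% | 12.5 | 17.9% |
| 45 min | 7.5 | 10.7% | 7.5 | 10.7% |

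Subtracting, AUC(five) − AUC(four) = 22.5 × C10 − 5 × Crest − 17.5 × C20. This needs no cortisol data and shows that the two are different measures.

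For scale only, assume cortisol of 10, 15, 13 and 11 at rest, 20, 30 and 45 minutes (arbitrary units, not from the documents). The four-point AUC is 225 + 412.5 + 162.5 + 82.5 = 882.5. Adding a 10-minute value of 12 gives 840 (−4.8%); a value of 20 gives 1020 (+15.6%).

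**3. Effect of an uneven log decision, same assumed values.**

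- Only the 20-minute sample logged: 882.5 − 27.5 × (15 − ln 15) = 544.5, a fall of 38.3%.
- Only the 45-minute sample logged: 882.5 − 7.5 × (11 − ln 11) = 818.0, a fall of 7.3%.
- All four logged: 176.3, a different scale altogether.

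Each is a change between weeks with no change in cortisol.

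**4. Illustration of the rule in a trial.** Assumptions, none from the documents except 60 women per arm (Sections 4.2 and 6.3): mean profile 9/16/14/11; log-scale SDs between women of 0.25, 0.30 or 0.40, between sessions of 0.15, 0.20 or 0.25, and between samples of 0.10; a distribution is logged if its skewness, arms pooled, exceeds 0.5, 0.75, 1.0 or 1.5, as a stand-in for inspection by eye; AR(1) model, no dropout, 4,000 runs per setting.

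| Result | Uneven rule | One scale |
|---|---|---|
| Log decisions disagree, no treatment effect | 3–93% of trials | none |
| Placebo arm shows significant change, no effect | 8–93% | 4–5% |
| Treatment-by-time type I error | 4.2–6.6% | 4.0–4.8% |
| Treatment-by-time power, active 15% lower, by SD set | 81–89%, 65–71%, 46–52% | raw 90%, 66%, 43%; logged 95%, 75%, 53% |

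Winsorizing at 2 SD, as planned, does not remove the problem: 8–93% against 5–7% on one scale.

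**The case against.** **On sampling.** Three procedural passages agree and only one differs, so a drafting slip in 9.4.3 is plausible. Section 9.4.3 describes the sampling; it does not name the AUC inputs one by one. The remark in 8.2 that "HPA-axis reactivity is reliably seen 10-30 minutes after cessation of the TSST" explains when a response is expected and is not a sampling time. This stands, and it limits the claim. A reader might infer that the AUC is definitely to be built with a 10-minute value, or that no AUC could be calculated if the schedule was followed. The documents support neither: a sample never scheduled is not naturally a missing value. But 9.4.3 is written in the past tense, its list is the only one in that section, and no passage says which set was followed.

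**On scale.** A single uniform transformation is a possible reading. Section 9.4.3 treats all AUCs as one interval-scaled repeated measure, which presupposes a common scale, so it would be too strong to say that the plan will mix scales. It permits mixing and does not exclude it. The homogeneity-of-variance and outlier checks in 9.4.1 might expose a wholly logged week, but no action is stated if they do. They could also miss a partial mix: in one simulated setting decisions disagreed in 39% of trials, while the largest weekly SD exceeded twice the smallest in only 14%.

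**On size.** The assumed SDs imply population skewness of 0.98, 1.22 and 1.67, and the cut-offs of 0.5 to 1.5 lie around those values. Disagreement is most frequent when the cut-off is near the assumed skewness and falls away elsewhere. The 8–93% range therefore mainly reflects the choice of assumptions and must not be read as a rate for this trial. The randomized comparison is little affected in the same runs. This objection stands in full.

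**Conclusion.** The point holds in two parts, both confined to the secondary cortisol endpoint.

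The sampling conflict rests on the text alone. The weight shifts follow from the protocol's own timings, on the assumption that the pre-stress sample is taken at the end of rest, as the procedural sections say.

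The scale gap rests on the literal wording of 9.4.1 and 9.4.3. Where scales are mixed, the within-arm time test and the hypothesis of change on active but not on placebo cannot be interpreted. How often this would arise depends on cortisol SDs and on a skewness judgement that the documents do not give; the simulated rates are illustration only.

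The treatment-by-time test is affected much less. That result assumes transformation decisions made with arms pooled, which the plan does not state. The primary endpoints, sample size and alpha are not affected.

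A reader might also infer that AUC with respect to ground is the wrong measure because it includes resting cortisol while Section 3 speaks of stress reactivity. That is a preference about a pre-specified measure, not an error. Adding an AUC with respect to increase would have to be squared with the statement in 9.2 that there will be no exploratory analyses. It forms no part of this point.

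**What to change.** Before unblinding:

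- **Sampling times.** Reconcile 1.2, 1.3 (footnote b), 8.2 and 9.4.3 on the cortisol times actually collected. State in 9.4.3 that the AUC is computed from that same set at every session, and define a missing timepoint against it.
- **Scale.** State in both 9.4.1 and 9.4.3 that one log-or-raw decision is made, blind to arm, and applied to every timepoint at every week before the AUC is calculated.

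The cost is wording only: no added participants, samples, tests or alpha. The downside is that, under one common decision, some single distributions may stay mildly skewed or be over-corrected. That is a small price for AUCs that can be compared between weeks.

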9.2 SAMPLE SIZE DETERMINATION

Sample size calculations were performed for the primary outcome measures. Correlation and effect size estimations were based on previously published literature ^{173,174}. With a sample size of N=120 and performing hypothesis tests at two-sided alpha=.05 and a correlation of >.25 among repeated measures, we have >90% power to detect a small effect size of .15.

The G*power software was used to determine the sample size ¹⁷⁵, based on a repeated measures ANOVA with within-between interaction ^{173,174}. We conservatively account for 15% (n =18) withdrawal following randomization, yielding 138 women who complete the protocol (powered for 120). This sample size will provide sufficient power to address secondary endpoints. No exploratory analyses will be performed.

By using proc mixed (not GLM), we will apply an analysis which is relatively robust to missing data. Before applying proc mixed, we will check for the randomness of missing data.

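### Section 9.4.3 discards a whole session's cortisol AUC when any one sample is missing, although the remaining samples are valid and could be used

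*Combined protocol and SAP*

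**What the plan says.** Section 9.4.3 defines the cortisol response as the AUC with respect to ground, by the trapezoid formula. Its missing-data rule is "In case of missing values for one or more single timepoints around the stress task, the AUC will not be calculated"; the session then counts as missing. The support offered is "The statistical procedures we will apply (proc mixed) are robust to randomly distributed missing data". No interpolation, imputation or sample-level analysis is given for cortisol. The unit of analysis is the session: "All AUC's will be treated as continuous, interval scaled measures and treated as repeated measure (assessed at weeks 8, 16, 20, and 24").

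The documents disagree on the number of samples per session. Section 9.4.3 has one pre-stress sample ("Before the stress test, a baseline, pre-stress serum sample was taken") and four afterwards ("reactivity serum samples were taken at 10-, 20-, 30-, and 45-minutes post-stress"), five in all. The Schedule of Activities (1.3) has four: "serum collected at the end of baseline rest and at minutes 20, 30, and 45 of recovery post-TSST". Section 8.2 also has four: "Plasma cortisol will be taken at the end of baseline rest and again during Recovery at minutes 20, 30, and 45". The schema in 1.2 agrees with these two.

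Section 9.2 allows for 15% withdrawal but not for lost blood samples, and asserts: "This sample size will provide sufficient power to address secondary endpoints".

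**The concern.** A failed draw or a spoiled tube is a routine event in serial blood sampling. Under this rule it removes the other three (or four) valid measurements of that visit as well. If the visit is week 8, the woman has no baseline AUC.

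The appeal to the mixed model does not repair this. A likelihood analysis is protected against missing data that depend on what was observed, but only on observations that enter the model. The samples drawn before the missing one are the data most likely to explain its absence, and they are dropped before the model is fitted.

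At stake is precision on the first-listed secondary endpoint. It measures the HPA axis, which section 2.2 presents as the candidate mediator and which section 4.1 puts in the central hypothesis.

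**Working it through.** **Inputs from the documents.** N = 120, two-sided alpha .05, correlation .25 (the floor of the stated range), effect size .15 and power above 90% for the repeated-measures within-between interaction (9.2). Four visits (9.4.3). Samples per session s = 4 (1.2, 1.3, 8.2) or 5 (9.4.3).

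**Assumed, because the documents give no figure.** Per-sample loss p; independence of losses except where clustering is stated; effect size .15 read as Cohen's f and applied to cortisol, although 9.2 set it for the primary outcomes.

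**1. The plan's own figure.** λ = f²·N·m/(1−r) = .0225 × 120 × 4/.75 = 14.4, with 3 and 3 × 118 = 354 degrees of freedom. The noncentral F gives power 90.2%, so the stated figure is reproduced.

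**2. Session AUCs lost under independence**, 1 − (1−p)^s:

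| p | 4 samples | 5 samples |
|---|---|---|
| 1% | 3.9% | 4.9% |
| 2% | 7.8% | 9.6% |
| 5% | 18.5% | 22.6% |
| 10% | 34.4% | 41.0% |

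At 5%, about 89 (or 109) of 120 × 4 = 480 sessions are lost. With four samples, the share of valid measurements in those discarded sessions is (.95 − .8145)/.1855 = 73%; with five it is 78%.

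**3. Clustered losses.** A failed line or a stopped session loses several samples together. With a beta-binomial model at p = 5% and four samples, the loss is 12.7% of sessions at an intra-session correlation of .3, 10.1% at .5, and 5% when losses always come together. With five samples the first two figures are 14.4% and 11.0%. Weaker clustering lies between these and independence.

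**4. Variance at 5% independent loss.** Generalised least squares information is averaged over all patterns of missing sessions, with each woman's other sessions kept and compound symmetry assumed. The mean shift is equal at weeks 16, 20 and 24 and scaled to f = .15. With four samples, the relative information for the arm difference in change is .787 at r = .25 and .772 at r = .50. The variance ratios are 1/.787 = 1.27 and 1/.772 = 1.30.

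**5. Power at N = 120, 5% independent loss, compound symmetry.**

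| r | no loss | 4 samples | 5 samples |
|---|---|---|---|
| .25 | 90.2% | 81.1% | 78.5% |
| .50 | 98.2% | 94.1% | 92.4% |

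Section 9.4.1 plans an autoregressive covariance instead. With an adjacent-visit correlation of .25, power is 83.8% before any loss and 74.0% or 71.3% after it. At .50 it is 93.1%, then 85.1% or 82.6%. The relative information with four samples is similar (.80 and .78).

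**6. If all drawn samples are used.** A session contributes nothing only when every sample is missing: .05⁴ = 0.000625% with four samples.

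**The case against.** The strongest reply is that the size of the loss is assumed. No document gives a loss rate, and independence is the costly end of the range. At 1-2% independent loss, only 4-8% of four-sample sessions go. This stands, and it is why a range is given.

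A reader might infer that a fifth of the women are lost. They are not: at 5% independent loss over 99.7% of women still contribute at least one AUC, and 81% (four samples) or 76% (five) contribute week 8 plus a later one. The variance and power figures already credit the retained sessions.

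A reader might also infer that the endpoint is underpowered. The documents do not support that as a general statement. The fall to about 80% belongs to correlation .25, the floor in 9.2. At .50 under compound symmetry, power stays above 92%.

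A third inference is that the rule biases the arm difference towards zero. It could do so if loss depends on cortisol level, but nothing in the documents shows such a link, and 9.2 requires a check on the randomness of missing data before the model is fitted. That check addresses possible bias; it does not recover the discarded samples.

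Finally, cortisol AUC is a secondary endpoint and section 9 specifies no mediation analysis, so its mechanistic weight comes from the rationale and not from the endpoint hierarchy.

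**Conclusion.** The rule is explicit, nothing elsewhere offsets it, and the loss is avoidable. Its size depends on an unstated loss rate. Under independence, about 4% to 34% of session AUCs are lost for assumed rates of 1% to 10% with four samples, or 5% to 41% with five. At 5% with four samples, clustering (intra-session correlation .3 or more) brings 19% down to between 5% and about 13%.

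At 5% independent loss the four-sample variance of the arm difference in change rises by about 27-30%. In the 9.2 setting, power falls from 90% to about 81% or 79%. The sufficiency claim for secondary endpoints is therefore not secured at the low end of the assumed correlation, though it is not refuted in general. Bias is a possibility only.

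The sampling-time conflict makes the rule more fragile. Read literally, a session run to the schedule always lacks the 10-minute sample that 9.4.3 lists, so no AUC could be calculated. This is a contradiction to be reconciled; it does not show that the sponsor means to discard every session. Overall this is a worthwhile, inexpensive improvement to a secondary analysis.

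**What to change.** 1. Reconcile the cortisol sampling times across 1.2, 1.3, 8.2 and 9.4.3.
2. In 9.4.3, replace the complete-session rule with an analysis that uses every drawn sample. One option is a mixed model on the individual cortisol values (arm × week × sample time, with participant and session covariance). Each arm-by-week AUC is then the trapezoid-weighted sum of fitted means. Interior weights are (next time − previous time)/2, end weights are half the adjacent interval, and all are set from the reconciled times. The other option is multiple imputation of single missing samples before the AUC is calculated.
3. State whether the log transformation and the 2 SD winsorizing apply to samples or to AUCs. With complete data the sample-level model gives the same point estimates as the current analysis only before winsorizing.
4. Keep the complete-session AUC as a sensitivity analysis, and report sample loss by arm, visit and sample time.

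The cost is revised wording, some extra SAS code, and a larger covariance or imputation model to estimate from about 120 women. No new data are needed.
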